11.1.3 Screening phase

Screening procedures will be performed up to 28 days before Day 1 of the first chemo-immunotherapy course, unless otherwise specified. All patients must first read, understand, and sign the IRB/REB/IEC-approved ICF before any study-specific screening procedures are performed. After signing the ICF, completing all screening procedures, and being deemed eligible for entry, patients will be enrolled in the study. Procedures that are performed prior to the signing of the ICF and are considered standard of care may be used as screening assessments if they fall within the 28-day screening window.

The following procedures will be performed during the screening visit:

- Informed Consent
- Review of eligibility criteria
- Medical history, demographics, and smoking history
- Complete physical exam
- ECOG Performance Status
- Weight and height
- 12-lead ECG (in triplicate if there are any significant abnormalities on the first ECG, each recording should be made 2-5 minutes apart)
- Review of prior/concomitant medications
- CT of the thorax and upper abdomen
- MRI of the brain
- Pulmonary function
- Cognitive function (MoCA test)
- HRQoL-questionnaire
- Pregnancy test in women of childbearing potential
- Collection of blood and stool samples for biomarker analyses including neuronal auto-antibodies
- Clinical laboratory tests for:
 - Hematology (see Table 4)
 - Clinical chemistry (see Table 5)
 - Creatinine Clearance
 - Serum pregnancy test (for women of childbearing potential only)

Hepatitis serologies

11.1.4 Treatment phase

Procedures to be conducted during the treatment phase of the study are presented in the SoAs. Screening procedures performed within 5 days of Day 1 of the first chemoimmunotherapy course do not need to be repeated before study treatment commences.

11.1.5 End of treatment

Assessments for patients who have completed durvalumab treatment and achieved disease control or have discontinued durvalumab due to toxicity in the absence of confirmed progressive disease, and for those who have progressed are provided below the schedule of events on page 11.

All patients will be followed for survival until the end of the study regardless of further treatments, or until the sponsor ends the study.

11.2 Patient reported outcomes (PRO)

11.2.1 Assessment of health-related quality of life (HRQoL)

HRQoL will be assessed using the European Organisation for Research and Treatment of Cancer (EORTC) Quality of Life Questionnaire (QLQ) C30 and the lung cancer specific module LC13. The QLQ-C30 measures fundamental aspects of HRQoL and symptoms commonly reported by cancer patients in general, the LC13 measures symptoms commonly associated with lung cancer and its treatment.^{61,62}

Patients will complete the questionnaires on paper. The questionnaires are either handed patients by local study personnel or mailed them from the central trial office in Trondheim. Patients will return the completed questionnaires in enclosed, prepaid envelopes provided by the central trial office. If patients who receive the questionnaires via mail do not return a completed questionnaire within 14 days, a reminder will be mailed.

When questionnaires are handed to patients by local study personnel, the study personnel will check that the questionnaire is completed correctly before they are stored locally. All questionnaires are mailed to the central trial office by completion of the trial or upon request from the trial office. If the questionnaires may not be mailed to the central trial office due to local laws or regulations, the local study personnel will enter the responses in the CRF.

11.3 Assessment of cognitive function

Cognitive function will be assessed using the Montreal Cognitive Assessment (MoCA).⁶³ The assessment will be performed by trained study personnel. The training is performed online at mocatest.org. Study personnel will enter the results in the CRF.

11.4 Biological sampling procedures

11.4.1 Collection of biological material for translational research

We will collect tumor samples, blood samples (whole blood, plasma, serum) and stool for biomarker analyses.

11.4.2 Tissue samples

We will collect diagnostic tissue samples and biopsies collected at relapse when possible to collect. We will collect formalin-fixed, paraffin-embedded and not fresh frozen tissue.

It is recommended that tissue samples are placed immediately (within 30 min of excision) into an adequate volume of 10% v/v neutral buffered formalin (NBF). Samples should remain in fixative for 24-48 hours at room temperature. It is vital that there is an adequate volume of fixative relevant to the tissue (at least a 10-volume excess) and that large specimens (if any) are incised prior to fixation to promote efficient tissue preservation.

An overnight processing schedule into paraffin wax is recommended, and FFPE blocks should be stored at ambient temperature and protected from light until shipment by courier at ambient temperature. FFPE blocks are stable under these conditions for an indefinite period.

The samples are to be shipped to the central trial office in Trondheim when enrollment of patients has

TRIPLEX
1.1
05-14N-2022

Norwegian University of Science and Technology

been completed or upon request.

Blocks of formalin-fixed, paraffin-embedded tissue is preferred, but slides are also welcome. Slides should be cut immediately before shipping, and the time point for shipping will be agreed upon with each site. Details on how to cut slides will be provided when shipping of blocks or slides is requested.

11.4.3 Blood samples

The following blood samples for biomarker analyses will be collected:

Serum

- 18 ml blood should be collected in 3 x 6 ml serum tubes (e.g. Vacuette Z serum clot activator tubes or similar) for isolation of serum.
- The tubes should be turned gently 8-10 times and left in a standing position at room temperature for 30-60 minutes.
- Centrifuge the tubes at 2500 g at room temperature for 10 minutes.
- After centrifugation, the serum should be aliquoted into 4 cryotubes, 1.5 ml in each. If more serum is available, increase the aliquots to 1.8 ml.
- All tubes should be labeled and stored at -80°C until shipment.

Plasma

- 30 ml blood should be collected in 5 x 6 ml EDTA tubes for isolation of plasma.
- The tubes should be turned gently 8-10 times to dissolve the anticoagulant.
- Centrifuge the tubes as soon as possible and within 60 minutes in a horizontal rotor (both swing-out and fixed rotors are ok) at 1600 g at 4°C for 15 minutes.
- After centrifugation, the plasma layer will be at the top of the tube. Mononuclear cells and platelets will be in a whitish layer, called the "buffy coat", below the plasma and above the red blood cells.
- Carefully collect the plasma with a sterile pipette (in a sterile hood) without disturbing the buffy coat layer and transfer the plasma to Eppendorf tubes.
- Centrifuge the Eppendorf tubes at 10 000 g at 4°C for 10 minutes, then transfer plasma into 4 x 4.5 ml cryotubes, up to 4 mL in each.
- Collect the buffy coat from all tubes and transfer to two cryotubes.
- All tubes should be labeled and stored at -80°C until shipment.

EDTA whole blood (only at inclusion)

- 6 ml blood should be collected in one EDTA tube for genetic analysis.
- The tube should be turned gently 8-10 times to dissolve the anticoagulant and aliquoted into 4 x 1.8 ml cryotubes with a minimum of 1 ml in each.
- All tubes should be labeled and stored at -80°C until shipment.

PAX tube

- 2.5 ml blood should be collected in one 10 ml PAX-tube.
- The tube should be turned gently 8-10 times and left in a standing position in room temperature for 2-3 hours before placed in freezer at -20°C for 24 hours. Do not store tubes in Styrofoam trays, as it could cause the tubes to crack.
- Transfer the tube to -80°C after 24 hours.
- All tubes should be labeled and stored at -80°C until shipment.

We are aware that not all sites have access to centrifuges with the descried capacity. The impact of centrifuge speed on the material quality is undetermined, and we will collect samples regardless of equipment. All sites will report the capacity of the centrifuges used for processing of blood samples. Labels for the tubes will be supplied from the central trial office in Trondheim.

Patients will be handed a kit for stool sampling including instructions for sampling. Patients will apply a sample on an appropriate medium and deliver at the study site in an envelope designed for this purpose. The stool samples should be labeled and stored at -80°C until shipment. Labels will be supplied from the central trial office in Trondheim. Details on stool sampling will be provided in the study procedure manual.

11.4.5 Proposed biomarker analyses

There are no established predictive markers for effect of ICI, chemotherapy or RT in SCLC. PD-L1 and TMB, the most relevant predictive markers in other types of cancer, do not appear to be clinically relevant in SCLC.

A molecular classification of SCLC based on RNA-sequencing has been proposed,⁶⁴ and there are indications that such classification might be used to predict treatment response.⁶⁵ Recently, a study found that germline genotype was associated with recurrence-free survival after platinum chemotherapy.⁶⁶ Thus, we will investigate the prognostic and predictive role of these molecular profiles in this trial.

Few have investigated the clinical role of ctDNA in SCLC, but data from NSCLC studies suggest that changes in ctDNA occur before response to immunotherapy can be evaluated on CT scans.⁶⁷ Thus, we will investigate the prognostic value of baseline ctDNA analyses (presence of detectable mutations and quantification), and associations between dynamics of known SCLC-related mutations in ctDNA are associated with response to therapy and treatment outcomes, especially long-term survival.

miRNA-profile is a highly relevant marker associated with extent of disease, tumor biology and prognosis. ⁶⁸ Few have investigated whether this is the case in SCLC. We will investigate associations between miRNA profile and the outcomes as described above - both for miRNA alone, and as part of an integrative model including both sequencing data from tissue, ctDNA and miRNA-analyses.

There are strong indications of associations between gut microbiome and response to ICI, ^{69,70} but this is scarcely investigated in SCLC. We assess the microbiome through sequencing, and investigate whether there are associations with the tumor, ctDNA or miRNA-profile - or treatment outcomes. To facilitate a correct interpretation, we will collect information about concomitant medication and use of antibiotics the last 6 months before study enrolment from all patients, since antibiotics are known to influence the gut microbiome.

We plan to start the biomarker analyses one year after enrolment in the trial has been completed. There is a lot of ongoing research on prognostic and predictive factors in patients who receive ICI, and based on research results published until then, other markers may be added to the analyses plan. A final plan describing analyses and techniques will be defined when enrolment is close to complete.

11.4.6 Withdrawal of informed consent for donated biological samples

If a patient withdraws, collection of data and biological material will stop, but according to Norwegian legislation, already collected data and material will be included in the analyses.

12. Disease evaluation and methods

The response to immunotherapy may differ from the typical responses observed with cytotoxic chemotherapy including the following (Wolchok et al 2009, Nishino et al 2013):

- Response to immunotherapy may be delayed
- Response to immunotherapy may occur after PD by conventional criteria
- The appearance of new lesions may not represent PD with immunotherapy
- SD while on immunotherapy may be durable and represent clinical benefit.

Based on the above-described unique response to immunotherapy and based on guidelines from regulatory agencies, e.g., European Medicines Agency's "Guideline on the evaluation of anticancer medicinal products in man" (EMA/CHMP/205/95/Rev.4) for immune modulating anticancer compounds, the study implements the following in addition to standard RECIST 1.1 criteria:

- PD must be confirmed after 4-6 weeks if study treatment continues beyond PD. If clinically significant
 deterioration occurs, a new CT scan should be performed earlier to ensure that patients are offered
 relapse treatment at a time when they still may benefit from other therapies.
- Patients may continue to receive durvalumab beyond confirmed PD in the absence of clinically significant deterioration and if investigators consider that patients continue to receive benefit from treatment.

Modification of RECIST as described may discourage the early discontinuation of durvalumab and provide a more complete evaluation of its antitumor activity than would be seen with conventional response criteria. Nonetheless, the efficacy analysis will be conducted based on the RECIST 1.1 criteria.

Of note, clinically significant deterioration which is not due to another known condition or intercurrent disease is considered to reflect a rapid tumor progression that necessitates treatment with anticancer therapy other than durvalumab or with symptomatic progression that requires urgent medical intervention (e.g. CNS metastasis, respiratory failure due to tumor compression, spinal cord compression).

12.1 Sensitivity analyses

One reason TRT is debated in ES SCLC, is that it may be problematic to offer palliative TRT for local relapse if patients receive TRT as part of their primary therapy. Thus, assessing the local relapse rate and time to local relapse is of great interest in this trial, since the survival benefit of TRT alone is limited, and that adding immunotherapy to chemotherapy may prolong local control. Another clinical setting of great interest is the timing and number of brain metastases. There are different policies with respect of timing of brain irradiation for brain metastases and the benefit of PCI in ES SCLC is debated.

Per RECIST 1.1 definition, irradiated lesions are not considered measurable. However, for this trial, we will perform sensitivity analyses including irradiated lesions for assessment of progression since these analyses will provide important information on how to care for ES SCLC patients. In these sensitivity analyses, irradiated lesions will be classified and measured similar to non-irradiated lesions according to RECIST 1.1.

13. Assessment of safety

13.1 Clinical laboratory tests

Blood samples for determination of clinical chemistry and hematology will be taken at the times indicated in the SoAs and as clinically indicated.

Clinical laboratory safety tests, including serum pregnancy tests, will be performed in a licensed clinical laboratory according to local standard procedures. Sample tubes and sample sizes may vary depending on the laboratory method used and routine practice at the site. Pregnancy tests may be performed at the site using a licensed test (urine or serum pregnancy test). Abnormal clinically significant laboratory results should be repeated as soon as possible (preferably within 24 to 48 hours).

The laboratory variables to be measured are:

Table 4 Hematology laboratory tests

Absolute neutrophile count	Hemoglobine	Leukocytes	Platelet count				
Table 5 Clinical chemistry (serum or plasma) laboratory tests							
Tuble 3 Clinical Chemistry (serum or plusma) laboratory tests							
Bilirubin	Aspartate aminotransferase (AST)		Alanine aminotransferase (ALT)				
Alkaline phosphatase (ALP)	Creatinine		Sodium (Na)				
Potassium (K)	Thyroid stimulating hormone (TSH)		Free thyroxine (FT4)				
Erythrocyte sedimentation rat	Lactate dehydrogenase (LDH)						
Tri-iodothyronine (T3) if abnormal thyroid function is suspected and FT4 is normal.							

Other safety tests to be performed at screening include assessment for hepatitis B surface antigen (HBsAg), hepatitis C antibodies (HCV Ab), and HIV antibodies.

If a patient shows an AST or ALT ≥3xULN together with total bilirubin ≥2xULN, refer to Section 13.15.2 for further instructions on cases of increases in liver biochemistry and evaluation of Hy's Law. These cases should be reported as SAEs if, after evaluation, they meet the criteria for a Hy's law case or if any of the individual liver test parameters fulfill any of the SAE criteria.

All patients should have further chemistry profiles performed at 30 days after permanent discontinuation of IP if the reason is an AE.

All patients with Grade 3 or 4 laboratory values at the time of completion or discontinuation from IP must have further tests performed until the laboratory values have returned to Grade 1 or 2, unless these values are not likely to improve because of the underlying disease.

13.1.1 Physical examinations

Physical examinations will be performed according to the assessment schedules (see the SoAs). Full physical examinations will include assessments of the head, eyes, ears, nose, and throat and the respiratory, cardiovascular, gastrointestinal, urogenital, musculoskeletal, neurological, dermatological, hematologic/lymphatic, and endocrine systems. Height will be measured at screening only. Targeted physical examinations are to be utilized by the Investigator on the basis of clinical observations and symptomatology. Situations in which physical examination results should be reported as AEs are described in Section 13.4.1.

Resting 12-lead ECGs will be recorded at screening and as clinically indicated throughout the study. ECGs should be obtained after the patient has been in a supine position for 5 minutes and recorded while the patient remains in that position.

At screening, a single ECG will be obtained on which QTcF must be <470 ms. In case of clinically significant ECG abnormalities, including a QTcF value >470 ms, 2 additional 12-lead ECGs should be obtained over a brief period (eg, 30 minutes) to confirm the finding before a patient in deemed ineligible.

First infusion

BP and pulse should be monitored:

- Prior to the beginning of the infusion (measured once from approximately 30 minutes before up to 0 minutes [i.e., the beginning of the infusion])
- Approximately 30 minutes during the infusion (halfway through infusion)
- At the end of the infusion (approximately 60 minutes ±5 minutes)
- If the infusion takes longer than 60 minutes, then BP and pulse measurements should follow the principles as described above or be taken more frequently if clinically indicated.

A 1-hour observation period is recommended after the first infusion of durvalumab.

Subsequent infusions

Patients should be carefully monitored with respect to BP and other vital signs prior to, during and post infusion as per institution standard and as clinically indicated.

13.2 WHO/ECOG performance status

ECOG performance status will be assessed at the times specified in the SoAs based on the following:

- 0 Fully active; able to carry out all usual activities without restrictions
- 1 Restricted in strenuous activity, but ambulatory and able to carry out light work or work of a sedentary nature (e.g., light housework or office work)
- Ambulatory and capable of self-care, but unable to carry out any work activities; up and about more than 50% of waking hours.
- 3 Capable of only limited self-care; confined to bed or chair more than 50% of waking hours
- 4 Completely disabled; unable to carry out any self-care and totally confined to bed or chair

5 Dead

13.3 Other safety assessments

If new or worsening pulmonary symptoms (e.g., dyspnea) or radiological abnormality suggestive of pneumonitis/ILD is observed, toxicity management as described in detail in the Toxicity Management Guidelines (see Appendix 1) will be applied. It is strongly recommended to perform a full diagnostic workup (including high-resolution computed tomography [HRCT], blood and sputum culture, hematological parameters, etc.), to exclude alternative causes such as lymphangitic carcinomatosis, infection, allergy, cardiogenic edema, or pulmonary hemorrhage. In the presence of confirmatory HRCT scans where other causes of respiratory symptoms have been excluded, a diagnosis of pneumonitis/ILD should be considered and the Dosing Modification and Toxicity Management Guidelines should be followed.

The Principal Investigator is responsible for ensuring that all staff involved in the study is familiar with the content of this section.

13.4 Safety parameters

13.4.1 Definition of adverse events (AEs)

The International Conference on Harmonization of Technical Requirements for Pharmaceuticals for Human Use (ICH) Guideline for Good Clinical Practice (GCP) E6(R2) defines an AE as:

Any untoward medical occurrence in a patient or clinical investigation patient administered a pharmaceutical product and which does not necessarily have a causal relationship with this treatment. An AE can therefore be any unfavorable and unintended sign (including an abnormal laboratory finding), symptom, or disease temporally associated with the use of a medicinal product, whether or not considered related to the medicinal product.

An AE includes but is not limited to any clinically significant worsening of a patient's pre-existing condition. An abnormal laboratory finding (including ECG finding) that requires an action or intervention by the investigator, or a finding judged by the investigator to represent a change beyond the range of normal physiologic fluctuation, should be reported as an AE.

AEs may be treatment emergent (i.e., occurring after initial receipt of investigational product) or nontreatment emergent. A non-treatment-emergent AE is any new sign or symptom, disease, or other untoward medical event that begins after written informed consent has been obtained but before the patient has received investigational product.

Elective treatment or surgery or preplanned treatment or surgery (that was scheduled prior to the patient being enrolled into the study) for a documented pre-existing condition, that did not worsen from baseline, is not considered an AE (serious or nonserious). An untoward medical event occurring during the prescheduled elective procedure or routinely scheduled treatment should be recorded as an AE or SAE. The term AE is used to include both serious and non-serious AEs.

13.4.2 Definition of serious adverse events (SAEs)

An SAE is an AE occurring during any study phase (i.e., screening, run-in, treatment, wash-out, follow-up), at any dose of the study drugs that fulfils one or more of the following criteria:

- Results in death
- Is immediately life-threatening
- Requires in-patient hospitalization or prolongation of existing hospitalization
- Results in persistent or significant disability or incapacity
- Is a congenital abnormality or birth defect in offspring of the patient
- Is an important medical event that may jeopardize the patient or may require medical intervention to prevent one of the outcomes listed above.

Medical or scientific judgment should be exercised in deciding whether expedited reporting is appropriate in this situation. Examples of medically important events are intensive treatment in an emergency room or

at home for allergic bronchospasm, blood dyscrasias, or convulsions that do not result in hospitalizations, or development of drug dependency or drug abuse.

The causality of SAEs (their relationship to all study treatment/procedures) will be assessed by the investigator(s) and immediately reported to the central trial office on the SAE form (i.e. no more than 24 hours after learning of the event) by emailing the completed SAE-form to [contact].

Exception An event that leads to hospitalization under the following circumstances should not be reported as an adverse event or a serious adverse event:

- Hospitalization for respite care
- Planned hospitalization required by the protocol (e.g., for study treatment administration or performance of an efficacy measurement for the study) or to perform study procedures
- Hospitalization for pre-existing conditions, provided that the hospitalization was planned prior to the study and the patient has not experienced an adverse event
- Hospitalization due solely to progression or suspicion of progression of the underlying cancer

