13.4.3 Definition of adverse events of special interest (AESI)

An adverse event of special interest (AESI) is one of scientific and medical interest specific to understanding of durvalumab and may require close monitoring. An AESI may be serious or non-serious. If the Investigator has any questions regarding an event being an immune-mediated AE (imAE), the investigator should promptly contact the Chief Investigator.

AESIs observed with durvalumab include:

- Diarrhea / Colitis and intestinal perforation
- Pneumonitis / ILD
- Hepatitis / transaminase increases
- Endocrinopathies (i.e. events of hypophysitis/hypopituitarism, adrenal insufficiency, hyper- and hypothyroidism and type I diabetes mellitus)
- Rash / Dermatitis
- Nephritis / Blood creatinine increases
- Pancreatitis / serum lipase and amylase increases
- Myocarditis
- Myositis / Polymyositis
- Neuropathy / neuromuscular toxicity (e.g. Guillain-Barré, and myasthenia gravis)
- Intestinal Perforations

Other inflammatory responses that are rare/less frequent with a potential immune-mediated etiology include, but are not limited to:

- Pericarditis
- Sarcoidosis
- Uveitis
- Other events involving the eye and skin
- Hematological events
- Rheumatological events
- Vasculitis
- Non-infectious meningitis
- Non-infectious encephalitis

It is possible that events with an inflammatory or immune mediated mechanism could occur in nearly all organs.

In addition, infusion-related reactions and hypersensitivity/anaphylactic reactions with a different underlying pharmacological etiology are also considered AESIs.

Further information on these risks (e.g. presenting symptoms) can be found in the current version of the durvalumab Investigator's Brochure. More specific guidelines for their evaluation and treatment are

described in detail in the Dosing Modification and Toxicity Management Guidelines (please see Appendix 1). These guidelines have been prepared by the Sponsor to assist the Investigator in the exercise of his/her clinical judgment in treating these types of toxicities. These guidelines apply to AEs considered causally related to the study drug/study regimen by the reporting investigator.

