13.9 Adverse events based on examinations and tests

The results from protocol-mandated laboratory tests and vital signs measurements will be recorded in the CRF. Deterioration as compared to baseline in protocol-mandated laboratory values and vital signs should therefore only be reported as AEs if they fulfill any of the SAE criteria or are the reason for discontinuation of study treatment.

If deterioration in a laboratory value or vital sign is associated with clinical signs and symptoms, the sign or symptom will be reported as an AE and the associated laboratory result or vital sign will be considered as additional information. Whenever possible, the reporting Investigator should use the clinical rather than the laboratory term (e.g., anemia versus low hemoglobin value). In the absence of clinical signs or symptoms, clinically relevant deteriorations in non-mandated parameters should be reported as AEs.

Deterioration of a laboratory value that is unequivocally due to disease progression should not be reported as an AE/SAE.

Any new or aggravated clinically relevant abnormal medical finding at a physical examination as compared with the baseline assessment will be reported as an AE.

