13.10 Disease progression

Disease progression can be considered as a worsening of a patient's condition attributable to the disease which is being studied. It may be an increase in the severity of the disease under study and/or increase in the symptoms of the disease. The development of new or progression of existing metastasis to the primary cancer under study should be considered as disease progression and not an AE/SAE. Events that are unequivocally due to disease progression should not be reported as an AE/SAE during the study.

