13.12 Deaths

All deaths that occur during the study treatment period, or within the protocol-defined follow-up period after the administration of the last dose of study drug, must be reported as follows:

- Death clearly resulting from disease progression should be reported to the Study Monitor/Physician at the next monitoring visit and should be recorded in the CRF. It should not be reported as an SAE.
- Where death is not due (or not clearly due) to progression of the disease under study, the AE
 causing the death must be reported to the Study Monitor/Physician as an SAE within 24 hours. It
 should also be recorded in the CRF.
- The report should contain a comment regarding the co-involvement of PD, if appropriate, and should assign main and contributory causes of death.
- Deaths with an unknown cause should always be reported as an SAE. It should also be recorded in the CRE
- A post-mortem may be helpful in the assessment of the cause of death, and if performed, a copy of the post-mortem results should be forwarded to the central trial office in Trondheim.

Deaths occurring after the protocol defined safety follow-up period after the administration of the last dose of study drug should be recorded in the CRF. If the death occurred as a result of an event that started after

the defined safety follow-up period and the event is considered to be due to a late onset toxicity to study drug, then it should also be reported as an SAE.

13.13 Reporting of serious adverse events and serious unexpected adverse reactions to the IRB and/or the Regulatory Authority

All SAEs must be reported, whether or not considered causally related to the investigational product. The Sponsor is responsible for informing the IRB and/or the Regulatory Authority of SAEs and SUSARs as per local requirements.

If any SAE occurs, investigators or other site personnel must inform appropriate Sponsor within one day i.e., immediately but no later than 24 hours of when he or she becomes aware of it.

For fatal or life-threatening adverse events where important or relevant information is missing, active follow-up is undertaken immediately. Investigators or other site personnel inform Sponsor representatives of any follow-up information on a previously reported SAE within one calendar day i.e., immediately but no later than 24 hours of when he or she becomes aware of it.

The reference document for definition of expectedness/listedness is the IB for durvalumab.

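### Section 13.4.2 exempts admissions for merely suspected progression from AE and SAE reporting, which contradicts the unequivocal-attribution rule in 13.9 and 13.10 and can delay or lose safety reports

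*Protocol*

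**What the plan says.** Section 13.4.2 makes an AE serious if, among other criteria, it "Requires in-patient hospitalization or prolongation of existing hospitalization". It then sets out exceptions, introduced by "An event that leads to hospitalization under the following circumstances should not be reported as an adverse event or a serious adverse event". The last exception listed is "Hospitalization due solely to progression or suspicion of progression of the underlying cancer".

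Three other sections address the same boundary between disease and adverse event:

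- Section 13.10: "Events that are unequivocally due to disease progression should not be reported as an AE/SAE during the study".
- Section 13.9, on laboratory values: "Deterioration of a laboratory value that is unequivocally due to disease progression should not be reported as an AE/SAE".
- Section 13.12, on deaths, requires an SAE report within 24 hours "Where death is not due (or not clearly due) to progression of the disease under study".

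On lung toxicity, section 13.4.3 names "Pneumonitis / ILD" as an AESI. For new or worsening pulmonary symptoms, or imaging that suggests pneumonitis, section 13.3 strongly recommends a full work-up "to exclude alternative causes such as lymphangitic carcinomatosis, infection, allergy, cardiogenic edema, or pulmonary hemorrhage".

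**The concern.** The exemption in 13.4.2 is wider than the rule in 13.10, and the extra width covers the uncertain cases. Take a patient admitted with new respiratory symptoms whose working label is suspected progression. A site following 13.4.2 files nothing. A site following 13.10 treats the event as reportable, because attribution to progression is not yet unequivocal. Both are following the protocol.

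Several features of this trial give the conflict weight:

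- Section 4.4 says there are no data on this combination and treats the comparison of side effects as an essential part of the trial. Section 5.1.1 does not rule out significant added toxicity from TRT.
- Under section 6.2 the DSMC reviews SAEs when 5, 15 and 30 patients have received three or more courses plus TRT, and then every 6 months. An event kept off the SAE form does not reach those reviews.
- Frequency and severity of AEs is a secondary endpoint (14.1), compared between arms (14.3.1). The exemption removes the event from AE as well as SAE reporting, so routine AE collection is not a backstop.
- Investigators know the allocation (9.1.1) when they choose between a label of progression and one of toxicity.

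**Working it through.** The plan states no figure on this point and no arithmetic applies. The check is a comparison of the rules.

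**Step 1: the standard of certainty in each section.**

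- 13.4.2, hospitalisation: progression or suspicion of it is enough, provided it is the sole reason for admission.
- 13.10, events in general: attribution to progression must be unequivocal.
- 13.9, laboratory values: attribution must be unequivocal.
- 13.12, deaths: a death that is not clearly due to progression is reported as an SAE.

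Three of the four resolve doubt in favour of reporting. Only 13.4.2 resolves it in favour of silence.

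**Step 2: one admission under both rules.** A patient is admitted with an untoward event. The only recorded reason is suspected progression.

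- On the day of admission, 13.4.2 exempts the event. Section 13.10 does not, because a suspicion is not unequivocal. The hospitalisation criterion is met, so without the exemption the 24-hour rule applies.
- If progression is then established beyond doubt, both sections exempt the event. There is no conflict.
- If pneumonitis, infection or another cause is then diagnosed, the event is an AE under 13.4.1. Pneumonitis is also an AESI under 13.4.3, and an event that required or prolonged the stay is an SAE under 13.4.2. It becomes reportable under either reading, but under 13.4.2 only from the diagnosis onward.
- If the question is never settled, or nobody revisits the label, 13.4.2 leaves the event unreported for good. Section 13.10 would have had it reported.

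The rules therefore diverge in two situations: the interval before the cause is known, and the case where it is never resolved.

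**Step 3: does any section decide between them?** None says which rule prevails. None states explicitly that an exempted admission must be reported once the suspicion is refuted.

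**Step 4: is suspected progression a reliable label here?** The protocol treats it with caution. Section 12 notes that new lesions under immunotherapy need not mean progression, and it requires confirmation after 4-6 weeks if study treatment continues beyond progression. Section 13.3 lists tumour spread in the lung among the alternatives to exclude when pneumonitis is considered, which acknowledges that the two can look alike.

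**The case against.** The strongest reply is that the text already contains the safeguards. The exemption is limited to admissions due solely to progression or its suspicion, and an admission with pneumonitis or infection is not that. Recognised pneumonitis is an AE, an AESI and, if it required or prolonged the stay, an SAE. The clock in 13.4.2 runs from learning of the event, and 13.6 collects the date on which an AE met an SAE criterion, so a later report is foreseen. New pulmonary symptoms are directed to a pneumonitis work-up by 13.3 and 13.4.4. Section 13.12 captures deaths not clearly due to progression, which limits the worst outcome.

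Most of this stands. It disposes of several stronger conclusions that a reader might draw:

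- *The protocol hides or exempts pneumonitis.* It does not; recognised pneumonitis stays reportable. Section 13.3 also runs from suspected pneumonitis to the exclusion of tumour spread, so it does not show that suspected progression suppresses pneumonitis reports.
- *Every such admission is lost.* Many would be reported once the diagnosis is made.
- *Only SAEs carry a 24-hour rule.* Overdose, potential Hy's Law cases, pregnancy and medication errors carry one too (13.15 and 13.16), and section 17 has AESI reports reviewed immediately at the central office.
- *A planned SAE comparison between arms is biased.* The protocol specifies no such comparison; the endpoint is AE frequency and severity. Open-label labelling could differ by arm, but nothing in the protocol shows that it would, or in which direction.

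What the reply does not remove is the contradiction. The word solely limits the exemption to admissions with no other stated reason, but an admission solely for suspected progression is exactly the case on which 13.4.2 and 13.10 disagree. The safeguards all depend on someone revising the label.

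**Conclusion.** The reporting rule is wrong as written because it contradicts itself. Section 13.4.2 exempts hospitalisations for suspected progression from AE and SAE reporting, while 13.10 and 13.9 exempt only what is unequivocally due to progression and 13.12 takes a similar line for deaths. This finding rests on the text alone and needs no assumption.

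The consequence is limited: reports of toxicity that first looks like progression can be late, or missing where the label is never revised. That touches the DSMC's SAE reviews and the secondary AE endpoint. It does not touch the primary endpoint, 1-year overall survival.

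The size cannot be stated. It would need the proportion of patients admitted for suspected progression and the proportion of those admissions with another cause, and the documents give neither. A count of lost events would be invented.

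**What to change.** In section 13.4.2, delete the words that extend the exemption to suspicion, and use the standard of section 13.10, so that only hospitalisation unequivocally due to disease progression is exempt.

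For clarity, add one sentence: an admission that was not reported because progression was presumed is reported within 24 hours of learning that progression is not confirmed. This makes explicit what the clock in 13.4.2 already implies.

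The change concerns reporting only and leaves clinical management as it is. It costs a wording amendment, a note to sites, and a few more SAE forms for admissions where progression is not yet certain.
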